4.16 What is the proposed frequency of analyses?

The analysis will occur at 24 months post-surgery. An interim analysis of data will take place once 6 months follow data is available for 50% of the cohort, in order to monitor for adverse events in the study group. Possible adverse events include hematoma formation in the shoulder, infection, and fracture of the greater tuberosity. Adverse events will be documented on standardized forms, including the severity of the adverse events. A data safety monitoring committee has been set up. The committee will consist of two surgeons, [name] and [name], both with extensive knowledge and experience in the area of shoulder and cuff surgery. Neither surgeon is involved in the trial. Any severe adverse events will be reported to the committee within one week of occurrence. At the time of interim analysis, the committee will determine, based on their collective experience, whether the trial should be stopped based on the frequency or severity of adverse events. The committee will review the interim analysis data primary outcome with the assistance of a statistician from the methods center. It is unlikely that the trial will be stopped due to demonstration of superiority, given the relative small numbers in the trial, but may be recommended by the committee if a difference is demonstrated at $p > 0.0001$.

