The primary outcome measure is the Western Ontario Rotator Cuff Index (WORC).(40)

The secondary outcome measures are the Constant Score(41), the American Shoulder and Elbow Society standardized assessment of shoulder function (ASES)(42). Ultrasound will be used to determine re-tear rates. MRI evaluations will be carried out to determine the healing status of the rotator cuff. The histological, molecular and cellular composition of the healing matrix, harvested at the time of the cuff repair, will be analyzed.

Null Hypothesis

There will be no difference in quality of life outcome in patients who undergo pre-operative bone trephination compared with pre-operative soft tissue trephination prior to arthroscopic rotator cuff repair at 24 months post-operatively.

Why is a trial needed now?

Rotator cuff repair carried out with current techniques has shown favourable results in terms of pain relief. However the re-tear rates remain high and are associated with significant morbidity in terms of functional outcome and shoulder strength. As rotator cuff disease becomes ever more prevalent with our aging population, it is imperative to determine if healing rates can be improved with autologous stem cell enhancement with pre-surgical preparation of the tendon insertion site through trephination. This trial is necessary both to provide optimal care of our patients, and to do so in a fiscally responsible fashion.

Give references to any relevant systematic review and discuss the need for your trial in the light of these reviews

An advanced search of the clinical databases in Medline and Pubmed was undertaken. There have been no systematic reviews or human comparative studies and only animal studies have been carried out to date. Favorable results in animal studies have been reported demonstrating the efficacy of growth factors, MSCs and cytokines to the insertion site in cuff repair. Hence the need for a study comparing the two different types rotator cuff insertion site preparation that may allow the benefit of local pluripotential stem cells as well as cytokines and growth factors to stimulate an increased healing response.

How will the results of this trial be used?

The results of the trial will provide valuable information regarding the best technique for managing the rotator cuff via repair. The data obtained from re-tear rates and quality of life measurements will enable

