4.7 What is the proposed frequency and duration of follow-up?

Patients are to be assessed in the clinic by the blinded evaluator at post-operative intervals of 3, 6, and 12 and 24 months post operatively. The primary outcome evaluation occurs at the 24 month evaluation. At each clinical follow up, the patient will be assessed with the clinical outcome measures. It is anticipated that at each clinic visit approximately 20 minutes will be spent with the assessor. However, as in all doctors' clinics, some waiting can be anticipated and this can be variable depending on clinic loads and nature of cases.

Radiographic analysis will be done with a high-resolution ultrasound at 6 and 24 months following surgical repair. An MRI T1 quantitative sequence will be carried out 6 weeks following surgical repair. An independent investigator trained in MSK radiology will perform evaluation of the imaging.

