4.14 Details of planned analyses

Primary:

Primary analyses involve a comparison of the mean WORC scores with control data from patients who have undergone an arthroscopic cuff repair, without trephination, obtained through our prospective database. This analysis is a two-tailed unpaired t-test to assess whether there is a statistically significant difference between groups for the mean WORC scores at all time points. The 5% significance level is employed. The underlying assumption for the WORC score data is that there is a normal distribution. If the sample distribution is determined to depart from normal, then a Wilcoxon rank sum test will be performed.

Secondary:

Similar analysis will be carried out for the functional outcome scores. The ASES, Constant Score, and U/S healing rates will be analyzed for differences at 24 months. The planned secondary analyses are performed using a 5% significance level. The secondary outcomes will be analyzed using appropriate statistics; t-tests for continuous and chi-square for dichotomous variables.

Interpretation of the MRI data will involve a comparison of the quantitative T1 signal intensity.

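### Section 4.16 prints its efficacy stopping threshold as p > 0.0001 where p < 0.0001 is evidently meant, and ties it to a primary outcome whose 24-month visit nobody will have reached at planned accrual

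*Combined protocol and SAP*

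**What the plan says.** Section 4.16 sets one interim look: "An interim analysis of data will take place once 6 months follow data is available for 50% of the cohort". Its stated purpose is "in order to monitor for adverse events in the study group". The section then adds an efficacy element: "The committee will review the interim analysis data primary outcome", helped by a statistician. On superiority it says "It is unlikely that the trial will be stopped due to demonstration of superiority, given the relative small numbers in the trial", but that a stop "may be recommended by the committee if a difference is demonstrated at $p > 0.0001". No other section gives or corrects an interim threshold.

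Section 4.16 names no WORC visit for this test. Section 4.7 states: "The primary outcome evaluation occurs at the 24 month evaluation". The statement of objectives, the primary research question and the null hypothesis also place the outcome at 24 months. Section 4.9 collects WORC before surgery and at 3, 6, 12 and 24 months. Section 4.14 describes the primary t-test as one "to assess whether there is a statistically significant difference between groups for the mean WORC scores at all time points".

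**The concern.** This is the monitoring committee's only written numeric threshold for efficacy, and as printed it says the opposite of what its own sentence requires. A demonstrated difference calls for a small p-value, whereas p above 0.0001 is what almost every trial gives, including one with no effect.

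Reversing the sign does not finish the job. The rule refers to the primary outcome, which the protocol evaluates at 24 months, while the look is triggered by 6-month data. If no 24-month scores exist at the look, the rule cannot be applied to the endpoint it refers to, and the committee must supply the visit itself. A stopping rule should be readable and executable before anyone sees interim data.

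**Working it through.** **Inputs.** SD 30.43, design difference 21.4 points, 33 per group raised to 45 per group for 25% dropout (4.10); 10% loss to follow-up (4.13); 60 recruited per year (4.11); 24 months of recruitment (4.18); 90 randomised and treated (4.10).

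**The plan's own figure.** A two-sided two-sample t-test at 5% with 33 per group has power 0.803 (0.791 with 32), so 33 per group is reproduced. 33 / 0.75 = 44, against the stated 45. Half of 90 is 45, or 22 to 23 per arm.

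**The threshold as printed.** With no effect, P(p > 0.0001) = 1 − 0.0001 = 0.9999. With a true difference of 21.4 points and 22 + 23 patients, P(p > 0.0001) = 0.958. Neither fits a stop that the protocol regards as improbable.

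**The threshold with the sign reversed.** Difference needed = t_crit × SD × √(1/n1 + 1/n2), two-sided at 0.0001. The crossing chance comes from the noncentral t distribution.

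| Per arm | df | t_crit | Points needed | Crossing chance at 21.4 | at 15 | at 10 |
|---|---|---|---|---|---|---|
| 22 | 42 | 4.298 | 4.298 × 30.43 × √(2/22) = 39.4 | 3.9% | 0.8% | 0.2% |
| 23 | 44 | 4.278 | 4.278 × 30.43 × √(2/23) = 38.4 | 4.4% | 0.9% | 0.2% |

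The 15- and 10-point effects are assumptions, and so is applying 21.4 points and SD 30.43 at the interim visit. A chance of about 4% or less agrees with the protocol's own expectation and its remark about small numbers. That supports p < 0.0001 as the meaning.

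**Cost in alpha.** One look at 0.0001 plus a final test at 0.05 gives at most 0.05 + 0.0001 = 0.0501.

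**Timing of the look.** Accrual is assumed uniform at r per year, counted from operation, with a fraction L lost before month 6. Placing all loss that early gives the latest look.

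- Patients needed = 45 / (1 − L) = 45, 50 or 60 for L = 0, 10% or 25%.
- Look month = 12 × needed / r + 6.
- Patients reaching 24 months = max(0, (look − 24) × r / 12).

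| r per year | Basis | Look month (L = 0, 10%, 25%) | Reached 24 months |
|---|---|---|---|
| 60 | 4.11 | 15, 16, 18 | 0, 0, 0 |
| 45 | 90 over 24 months, 4.18 | 18, 19.3, 22 | 0, 0, 0 |

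Any 24-month data at the look require accrual below 12 × needed / 18 = 30, 33 or 40 per year for the three loss rates. Both planned rates are above all three.

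**Where this stops holding.** Section 4.10 reports about 50% withdrawal, largely before randomisation. If the 60 per year are consented patients and only 30 per year are treated, the look moves to month 24, 26 or 30, with 0, 5 or 15 patients past 24 months. Even then few 24-month scores exist.

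**The case against.** The sign is one machine-read character, and a reading error cannot be excluded from this text. If the page shows the opposite sign, that half of the point falls away; the missing visit remains. If the sign is a true misprint, its context largely corrects it: the sentence speaks of a demonstrated difference, the stop is discretionary, and a statistician assists. A reader might infer that the committee would actually stop on p > 0.0001. The documents do not support that.

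A reader might also infer that the visit is wide open among 6 months, 24 months and every visit. That is too strong. The 6-month trigger makes the 6-month WORC the natural reading, the null hypothesis and section 4.7 fix the endpoint at 24 months, and the all-visits wording in 4.14 describes the planned analysis rather than the interim rule. What stands is narrower: 4.16 does not name the visit, and the visit that its reference to the primary outcome points to cannot be used at planned accrual.

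A third inference would be that the look inflates type I error. At 0.0001 for one named visit it does not, beyond 0.0001.

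Finally, 4.14 compares WORC with database controls, whereas the research question and null hypothesis compare bone with soft tissue trephination. That is a separate conflict and is not counted against 4.16. The crossing chance against database controls cannot be derived, because the documents do not give the number of controls.

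**Conclusion.** The point holds as a minor but real correction. As printed, the threshold contradicts its own sentence; p < 0.0001 is evidently meant, subject to a check of the source page. Separately, the rule as worded cannot be applied to the 24-month primary endpoint at planned accrual, because the look comes at about month 15 to 22 with no 24-month WORC, and 4.16 does not say that the 6-month score is meant.

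The practical consequence is small. For the randomised comparison, the corrected rule needs about 39 points and would be crossed about 4% of the time at the full design effect. That rests on SD 30.43 and 21.4 points holding at the interim visit and on 22 to 23 patients per arm with data. The timing result rests on uniform accrual at the planned rates. The sample size and the final test are unaffected.

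**What to change.** Check the sign in 4.16 against the source page. If it is printed as p > 0.0001, correct it to p < 0.0001. In the same sentence, state that the interim test uses the 6-month WORC and that the final test stays at 5%, the alpha cost being at most 0.0001. The downside is that a stop would rest on an earlier visit than the 24-month endpoint.

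If the sponsor does not want that, the alternative is to delete the efficacy clause and limit the look to adverse events, its stated purpose. The downside is that a small chance of an early efficacy stop is given up. Adopt one of the two, not both.

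Either way the cost is an amendment of one or two sentences in 4.16 and matching instructions to the monitoring committee, with no added patients, visits or procedures.

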4.18 What is the estimated cost and duration of the trial?

The duration of the trial will be 48 months total – 24 months of recruitment and 24 year for patients to reach the endpoint of the study. Please see attached budget for associated costs.

DETAILS OF TRIAL TEAM

Trial management:

What are the arrangements for day to day management of the trial?

The orthopedic research study coordinator is responsible for the day to day management of the trial. This includes: general administrative details, implementing randomization, collecting, monitoring, tracking and analyzing data. The Study Research Coordinator (SRC) has experience in biostatistics, computer technology, epidemiology and study management. He/she is available to answer questions on a daily basis. **Quality Monitoring:** Forms: All forms are checked by the SRC for completeness, consistency and extreme values. **Appointments:** The SRC is responsible for monitoring participant visits **Equipment:** The scales used to measure power are calibrated. **Data Management:** is supervised by the study biostatistician. Data is collected on standardized Case Recording Forms (CRF). Any revisions to the CRF's are dated to maintain an audit trail of these changes. CRF's are signed and dated by the clinical investigator.

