4.3 Proposed practical arrangements for allocating participants to trial

A treatment allocation schedule will be produced under the supervision of the orthopedic research study coordinator. Allocation to either bone trephination or soft tissue trephination will occur in blocks of 10 in a randomized fashion. Treatment allocation will be determined when the patient is scheduled for surgery. Treatment allocation will be stratified by surgeon.

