4.4 What are the proposed methods for protecting against sources of bias?

Blinding: Due to the nature of a surgical trial, the surgeon may not be blinded to the intervention. However, a trained MSK radiologist will carry out the post-operative imaging, both ultrasound and MRI, and will be blinded to the nature of the treatment. Further, an independent assessor will carry out the follow-up functional assessments and will be blinded. This will minimize the potential for biases introduced by the examiner when performing the physical assessment and recording data. The assessor will not have access to the patient chart prior to the examination. The patient will also be blinded to the treatment assignment. To help reduce the potential for observer bias, the physical examination and the administration of study questionnaires are standardized.

Control of contamination and co-intervention:

Co-interventions will be documented. These are to include physiotherapy including the number of sessions and the nature of the physiotherapy intervention. The type and frequency of pharmaceutical agents used by the patient post-operatively will also be documented. In addition, all intraoperative adjunctive procedures will be documented, as well as details of the treatment method and implants used.

Ensuring complete follow-up: The following measures will help to ensure completion of follow-up: a) study patients will supply their own address, telephone, and email information, and the name, relationship, address, telephone, and email information of someone who does not reside with the patient, but is likely to have contact with them should they move or change telephone information, b) patients will receive a copy of the consent form which will outline the purpose of the study, the importance of their individual participation and attendance for follow-up assessments, and c) the research coordinator will maintain regular contact with the patients.

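### One role holds the allocation and also checks and analyses the outcome data, so cleaning and analysis of the bone versus soft-tissue comparison are not protected by blinding

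*Combined protocol and SAP*

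**What the plan says.** **Duties of the coordinator.** Section 4.3: "A treatment allocation schedule will be produced under the supervision of the orthopedic research study coordinator". The trial management section (under Details of Trial Team) uses the same job title: "The orthopedic research study coordinator is responsible for the day to day management of the trial". It lists the duties as including "implementing randomization, collecting, monitoring, tracking and analyzing data". On quality monitoring it adds: "All forms are checked by the SRC for completeness, consistency and extreme values". Section 4.4, on completeness of follow-up, says that "the research coordinator will maintain regular contact with the patients".

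**Who is blinded.** Section 4.4 covers three parties:
- the radiologist: "a trained MSK radiologist will carry out the post-operative imaging, both ultrasound and MRI, and will be blinded to the nature of the treatment";
- the functional assessor: "an independent assessor will carry out the follow-up functional assessments and will be blinded";
- the patient: "The patient will also be blinded to the treatment assignment".

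Section 4.9 adds that the research assistant who helps patients with the WORC is blinded.

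**Other oversight.** In the trial management section the study biostatistician supervises data management, CRF revisions are dated, and the clinical investigator signs the CRFs. None of these is described as blinded. Section 4.16 gives a methods-centre statistician a part in the interim review only.

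**The concern.** Section 4.4 protects the measurement of outcomes but not what happens to the data afterwards. Someone who oversees the schedule and implements randomisation can know each patient's arm. If the same person reviews outcome forms and analyses them, judgements made during cleaning and analysis are made with the arm known.

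The plan leaves room for such judgements. It does not define an extreme value or say what follows when one is found. Section 4.14 lets the observed distribution decide between the t-test and the Wilcoxon test, without naming a criterion or who applies it. The primary outcome is a patient-reported score compared between small groups, so a few handling decisions could matter in a borderline result. This is a different matter from whether the allocation sequence can be guessed. It arises after randomisation and would remain whatever the block size.

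**Working it through.** **Step 1: trace the duties.**

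| Duty | Role | Where | Blinding stated? |
|---|---|---|---|
| Supervises allocation schedule | Orthopedic research study coordinator | 4.3 | No |
| Implements randomisation | Same title | Trial management | No |
| Analyses data | Same title | Trial management | No |
| Checks all forms, including for extreme values | Study Research Coordinator (SRC) | Trial management | No |
| Supervises data management | Study biostatistician | Trial management | No |
| Supports WORC completion | Research assistant | 4.9 | Yes |
| Functional assessment | Independent assessor | 4.4 | Yes |
| Imaging | Radiologist | 4.4 | Yes |

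The first three rows carry the same job title, so the conflict between knowing the allocation and analysing the data does not depend on equating titles. The fourth row relies on reading SRC as the same post, as the trial management paragraph does. Masked arm codes, separate custody of the schedule and a database lock before unblinding are not described anywhere.

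**Step 2: confirm the plan's sample size, which sets the scale.** Inputs from 4.10: SD 30.43, difference 21.4, two-sided alpha 0.05, power 0.80.

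- Normal approximation: n = 2 × (1.960 + 0.842)² × (30.43 / 21.4)² = 31.7, rounded up to 32 per group.
- Exact two-sample t-test: 32.7, rounded up to 33 per group, which reproduces the plan's figure.

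**Step 3: illustrate the possible size.** Assumption, not in the documents: k values in one arm are each moved by 60 points in the same direction. Sixty points is 60 / 30.43 = 2.0 SD.

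- Shift in arm mean = k × 60 / 33. For k = 1 this is 1.8 points; for k = 3 it is 5.5 points.
- SE of the difference = 30.43 × √(2 / 33) = 7.5 points.
- Shift in SE units: 1.8 / 7.5 = 0.24 and 5.5 / 7.5 = 0.73.
- Shift relative to the target: 1.8 / 21.4 = 8% and 5.5 / 21.4 = 26%.

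Three values could decide a borderline test but could not create the target difference.

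**The case against.** The strongest reply is that the important assessments are blinded. The WORC is completed by a blinded patient with a blinded research assistant at hand, the assessor and radiologist are blinded, and a biostatistician supervises data management. This stands and limits the exposure to cleaning and analysis. It does not close the gap, because the supervision is not described as blinded and analysis remains on the coordinator's list.

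Some stronger readings are tempting, and the documents do not support them.

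- **That the blind fails.** The plan never promises a blind in data handling, so none is broken. What can be said is that this stage is unprotected.
- **That the coordinator may alter or drop WORC values.** The text says only that forms are checked. No section permits values to be changed or excluded.
- **That the coordinator could chase follow-up differently by arm.** Section 4.13 gives reminder calls to the research assistant and calls after a missed re-booking to the surgeon. The coordinator monitors visits and keeps in touch with patients, which is too little to carry this claim.
- **That the whole primary analysis is exposed in the same way.** Section 4.14 sets the primary analysis against database controls who had no trephination. Masking bone against soft tissue does little there. The point bears on the between-arm comparison, which section 4 states as the primary research question and null hypothesis.

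It is also fair to say that the 60-point example shows what is arithmetically possible, not what is likely.

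**Conclusion.** The concern holds in limited form. As the duties are assigned, the role with access to the allocation also checks and analyses the outcome data, and no described safeguard blinds those steps for the bone versus soft-tissue comparison. This is a stated assignment of duties, not an omitted detail.

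The size cannot be estimated from the documents. The illustrative shifts of 1.8 and 5.5 points rest on the assumed 60-point changes, on 33 analysed per arm and on the plan's SD of 30.43. The conclusion itself rests on the traced duties and on no figure. It should be corrected because the remedy is cheap, although the plan does not show that any bias has occurred.

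**What to change.** Amend section 4.3, section 4.14 and the trial management section as follows.

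1. **Separate the duties.** Whoever holds the schedule and implements randomisation does not clean or analyse outcome data. For example, the coordinator keeps randomisation and the operative and treatment forms. The blinded research assistant checks the WORC, ASES and Constant forms under the biostatistician's supervision. Hiding only the allocation field from the coordinator would not be enough, because that role checks all forms and section 4.4 requires treatment details to be recorded.
2. **Keep the schedule away from the interim statistician.** That person helps the committee review the primary outcome under 4.16, so holding the schedule would join allocation and outcome data again.
3. **Lock before merging.** Resolve all extreme-value checks and lock the outcome database before arm codes are added.
4. **Mask the between-arm analysis.** The study biostatistician, not the coordinator, runs it on arms coded A and B, with the t-test or Wilcoxon choice fixed before the codes are opened.
5. **Database-control comparison.** Coding helps little here, so fix the choice of test in advance.

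The cost is protocol wording, some redistribution of duties among roles already named, and one coded data transfer. No additional patients or procedures are needed.
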